- (ii) Non-drug treatments/therapies (conventional, alternative, and experimental) currently used to relieve neck/shoulder pain, including duration and frequency of use/application
- (iii) Over the counter and prescription medications currently used, and therapies currently engaged in for any non-pain relief indication, including duration, dosage, and frequency of use

SUBJECT DEMOGRAPHICS: Age, gender, and ethnicity

OUTCOME ASSESSMENT TOOLS

VISUAL ANALOG SCALE (VAS) DEGREE OF PAIN RATING

Subjects will be asked to rate the overall degree of pain experienced in the neck / shoulder region on the following 0-100 mm (0 -10 cm) Visual Analog Pain Scale, by responding to the following question:

“Using the scale below, please mark with a cross (X) a SINGLE SPOT along the 0 to 100 line below that best shows how much **pain you feel in your neck / shoulder** right now. ‘0’ means you feel no pain at all and ‘100’ means you feel the worst pain imaginable. PLEASE MARK ONLY ONE SPOT. DO NOT THINK OF OR WRITE IN A NUMBER.”

no pain worst pain imaginable
0 100

The Visual Analog Pain Scale (VAS) is one of the three most commonly used scales for assessing chronic pain. It is a simple scale that consists of a line anchored at one end by a label such as "NO PAIN" and at the other end "WORST POSSIBLE PAIN". The subject marks on the line the spot for the pain intensity, which is then measured.

Standard guidelines for effective use of the VAS that are followed in this clinical study are:

- i. The line should be 10, 15 or 20cm long, as other lengths are less reliable.
- ii. There should be a small vertical mark at each end, with numbers 0 and 100, and a verbal description.
- iii. The verbal description must be in absolute terms (e.g., worst pain imaginable);
- iv. The line itself should be clear of any markings and should be horizontal rather than vertical, for more reliable measurements.

Used in the above way, it has been shown that the VAS is a proper ratio scale. Like a thermometer, this means that its two ends are rooted, and a doubling of the score does accurately reflect a doubling of the pain. Consequently, sensitive t-tests and ANOVA methods can be used in the analysis, so that significant differences can be identified with relatively small sample sizes or small differences between groups.

Source: *Measuring Pain* by Adrian White, *Acupuncture in Medicine*, November 1998 – Vol 16 No. 2

LINEAR RANGE OF MOTION (ROM) MEASUREMENTS

Mobility in the neck/shoulder region will be measured using a universal inclinometer, as follows:

- (i) Shoulder ROM will be measured from a seated passive abduction, the relaxed position of parallel to the side of the body through full extension above the head. Maximum movement is 180 degrees.
- (ii) Neck ROM will be measured in a supine position, from forward position to face over shoulder. Maximum movement is 90 degrees.

SUBJECT SATISFACTION WITH STUDY OUTCOME

The subject is asked to rate how satisfied he or she is with any change in neck/shoulder pain following completion of the laser administration procedure with the Erchonia Lasers by using the 5-point Likert scale below to respond to the following question: "Overall, how satisfied or dissatisfied are you with any change in the pain in your neck and/or shoulder following the study treatment with the study laser devices?"

- Very Satisfied
- Somewhat Satisfied
- Neither Satisfied nor Dissatisfied
- Not Very Satisfied
- Not at All Satisfied

STUDY PROCEDURE PROTOCOL

PRE-TREATMENT ACTIVITIES

Pre-treatment activities will be performed at the study site prior to administering the sequential Erchonia® PPL blue laser therapy followed by the standard Erchonia XLR8 red laser therapy.

STUDY QUALIFICATION

SIGNING OF INFORMED CONSENT FORM

The PI will commence by presenting and reviewing in detail the items in the informed consent form with the individual and answer any questions. To proceed, the individual must willingly sign the informed consent form.

ASSIGNMENT OF SUBJECT IDENTIFICATION NUMBER

The subject is assigned a unique de-identified subject identification number based upon his or her order of entry into the study. The Subject ID number will comprise the initials of the test site Principal Investigator's first and last name followed by a single digit number that represents the test site number (e.g. test site #1 = 0, test site #2 = 1, etc.) and then a two-digit number that represents the subject's order of entry in the study.

For example, the 14th subject to be enrolled at test site #2 with Principal Investigator John Black will have a Subject ID of JB114.

STUDY QUALIFICATION EVALUATION: INCLUSION/EXCLUSION CRITERIA

INCLUSION CRITERIA

To be eligible for study participation, a subject must satisfy each of the following criteria.

1. Signed informed consent form
2. 22 years of age or older
3. Primary language is English
4. Subject presents with one or more of:
 - chronic neck pain on the right side of the neck and/or the left side of the neck and/or the back of the neck; and/or
 - chronic shoulder pain on the right shoulder and/or the left shoulder.
5. Subject is diagnosed with one or more of the following:
 - Osteoarthritis: Degenerative Joint Disorder (DJD)
 - Chronic Muscle Spasms
 - Cervical and Thoracic Spine Sprain Strain

... based on the following criteria specific to each condition:

- Patient History
- Medication Use History
- Records Review: where available, such as x-ray, MRI, and CAT scan reports

- Physical Examination

Specific criteria to diagnose each condition are as follows:

A. Osteoarthritis: Degenerative Joint Disorder (DJD)

- Patient History: Previous trauma or infection to the area.
- Medication Use History: Anti-inflammatory medications; either over the counter (e.g., Advil, Motrin, Aspirin); prescription medications (e.g., Celebrex, Vioxx)
- Previous Records Review: DJD indicated.
- Physical Examination: Pain and pain with ROM evaluation; reduced ROM, particularly passive ROM motion; cracking/popping/creaking sound upon movement (ROM); possible joint swelling; possible bone spurs (osteophytes).

B. Chronic Muscle Spasms

- Patient History: Previous trauma; “frozen” shoulder and/or neck; history of restricted range of motion; pain relief through heat application and/or physical manipulations such as massage and physical therapy.
- Medication Use History: Over the counter/prescription muscle relaxers and palliatives.
- Previous Records Review: Lack of DJD indicated.
- Physical Examination: Limited ROM; muscle tightness/knotting; tenderness and pain upon palpation; possible radiation pain upon palpation of tender spots (trigger points).

C. Cervical and Thoracic Spine Sprain Strain

- Patient History: Injury or pain initiated after motion or repetitive motion and exacerbated by motion; history of an old injury that can be exasperated acutely; pain and weakness on flexion; increased joint pain at the end range of motion.
- Medication Use History: OTC and/or prescription muscle relaxants or anti-inflammatory medications.
- Previous Records Review: Muscle or ligament injury indicated.
- Physical Examination: Pain that worsens with movement (active and/or passive ROM); reduced ROM; muscle weakness; stiffness; tenderness upon palpation; possible swelling.

6. Pain is chronic: symptoms have persisted for longer than the past 30 days
7. Subject's self-reported Degree of Pain rating on the 0-100 VAS pain scale is 50 or greater.
8. Subject is willing and able to refrain from consuming any over the counter and/or prescription medication(s) and/or herbal supplements intended for the relief of pain and/or inflammation, including muscle relaxants throughout the course of study participation
9. Subject is willing and able to refrain from engaging in any non-study procedure therapies for the management of his or her neck/shoulder pain throughout the course of study participation, including conventional therapies such as physical therapy, occupational therapy and hot or cold packs, as well as alternative therapies such as chiropractic care and acupuncture

EXCLUSION CRITERIA

A subject who satisfies any of the following criteria will be excluded from study participation:

1. Presenting primary pain is located outside or in addition to the region of the neck (right side/left side/back) or the shoulder (right and/or left side)
2. Etiology of neck/shoulder pain cannot be definitively diagnosed; or has been diagnosed as being in whole or in part other than that of osteoarthritis, chronic muscle spasms or cervical and thoracic spine sprain strain; or other potentially contributing etiologies cannot be satisfactorily ruled out
3. Pain is acute: symptoms prevailed for fewer than each of the prior 30 days
4. Current active chronic pain disease: such as chronic fatigue syndrome and fibromyalgia
5. Use of analgesics or muscle relaxants within 7 days prior to study procedure administration
6. Use of systemic corticosteroid therapy (inhaled and topical corticosteroids permitted), narcotics or Botulinum toxin (Botox®) injection in the neck / shoulder region within 30 days prior to study procedure administration
7. Active cancer or treatment for cancer within the last 6 months
8. Unstable cardiac disease, such as recent cardiac arrhythmia, congestive heart failure or myocardial infarction
9. Prior surgery to the neck/shoulder region
10. Known herniated disc injury
11. Active infection, wound or other external trauma to the areas to be treated with the laser
12. Medical, physical, or other contraindications for or sensitivity to light therapy
13. Serious known mental health illness such as dementia or schizophrenia; psychiatric hospitalization in the past two years
14. Pregnant or breast feeding
15. Participation in a research study within the past 30 days

PRE-TREATMENT EVALUATIONS

The pre-treatment evaluation phase directly follows successful study qualification, on the same day.

BASELINE VARIABLES

- Neck / Shoulder Pain Variables
- Concomitant Medication and Therapy Use
- Subject Demographics

OUTCOME ASSESSMENTS

- Visual Analog Scale (VAS) Degree of Pain Rating
- Linear Range of Motion (ROM)

TREATMENT ADMINISTRATION PHASE

TREATMENT ADMINISTRATION PROTOCOL

- The treatment administration phase of the study directly follows successful completion of the pre-treatment evaluation phase, on the same day.
- The treatment administration phase comprises a single sequential treatment administration session with the Erchonia® PPL blue laser therapy followed by the standard Erchonia red laser therapy using the Erchonia XLR8.
- The total treatment administration time is eighteen (18) minutes.
- The treatment is administered at the test site.
- The subject enters the treatment room, is seated comfortably, and correctly fitted with the protective eyewear.

The treatment administration protocol is as follows:

(i) Erchonia PPL blue laser therapy treatment administration protocol:

The single treatment administration protocol commences with the blue laser therapy treatment protocol using the Erchonia PPL and is as follows:

1. The Erchonia® PPL device is positioned approximately 2 to 3 inches from the initial targeted treatment area of the left shoulder, then activated.
2. The pulsed PPL laser treatment is administered by using a slow sweeping motion beginning at the left shoulder, moving across the cervical spine, and continuing to the right shoulder maintaining the distance from the skin surface of approximately 2 to 3 inches throughout the process.
3. This motion is then reversed, sweeping from the right shoulder back across the cervical spine to the left shoulder, again maintaining the distance from the skin surface of approximately 2 to 3 inches throughout the process.
4. This bidirectional sweeping technique is continuously performed until the device turns off which is a total duration of five (5) minutes.

(ii) Erchonia XLR8 standard red laser therapy treatment administration protocol:

Immediately following completion of the treatment administration with the Erchonia PPL blue laser therapy, the treatment administration with the standard Erchonia XLR8 red laser therapy commences. The red laser therapy treatment administration protocol is identical to that in the retrospective comparative control study, and is as follows:

1. The Erchonia® XLR8 is positioned and centered 6 inches above the subject's sagittal suture (top of the head), then activated.
2. One minute of pulsed laser is applied to the sagittal suture (top of the head)
3. The next treatment area is the left cervical, shoulder and torso area. The laser is applied starting in the cerebral region, at the top of the ear, lasering the left cervical anterior and posterior muscles, then working the laser down over the left shoulder and torso anterior and posterior muscles, maintaining the laser 6 inches from the skin. This part of the treatment takes two (2) minutes.
4. Step 3 is repeated to the subject's right cervical, shoulder and torso area for 2 minutes.

5. One minute of pulsed laser is then applied to right shoulder during passive external rotation of the shoulder. The anterior muscles of the right shoulder (pectoralis group) are lasered, with the subject's arm bent at the elbow.
6. One minute of pulsed laser is then applied to the right shoulder during passive adduction of the subject's right arm and shoulder. The posterior muscles of the right shoulder are lasered.
7. One minute of pulsed laser is then applied to the right cervical muscle and trapezius muscle during passive left lateral flexion of the cervical spine. Starting in the neutral position of the head, the laser light is applied to the right cervical muscles and right trapezius muscles.
8. One minute of pulsed laser is then applied to the right sternocleidomastoid and scalene muscles during passive range of motion. The laser light is applied to the right sternocleidomastoid and scalenus muscles.
9. Step 5 is then repeated to the left shoulder.
10. Step 6 is then repeated to the left shoulder.
11. Step 7 is then repeated to the left cervical spine.
12. Step 8 is then repeated to the left sternocleidomastoid and scalenus muscles.
13. The subject's protective eyewear is removed, and the single treatment administration session is over.

JUSTIFICATION FOR THE TREATMENT ADMINISTRATION PROTOCOL

The treatment administration protocol with the red laser device in this current study is identical to that which was evaluated in the comparative retrospective study to enable direct comparison of findings between the two studies and statistical analysis of different group outcomes. The only modification in the current study is the addition of a 5-minute treatment with the Erchonia PPL laser, administered immediately prior to the red laser therapy which is the treatment arm being evaluated for non-inferiority.

TREATMENT ADMINISTRATION PHASE EVALUATIONS: STUDY ENDPOINT

Within three (3) minutes of completion of the procedure administration phase, study endpoint evaluation will occur.

OUTCOME ASSESSMENTS

- Visual Analog Scale (VAS) Degree of Pain Rating
- Linear Range of Motion (ROM)
- Subject Satisfaction with Study Outcome Rating
- Adverse Events Evaluation

POST-TREATMENT ACTIVITIES

The post-treatment evaluation phase of this study will commence immediately following completion of the treatment administration phase evaluations and will last for two (2) days (48 hours).

The post-treatment outcome assessments will be recorded by the subject in his or her own home on forms provided by the test site. The subject will be instructed on when and how to complete the forms and how to return them to the test site prior to leaving the test site on the treatment administration day.

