Appendix A: Recruitment Advertisement

Appendix B: Informed Consent Form

Appendix C: Case Report Forms

STUDY INFORMATION

SPONSOR

Erchonia Corporation
[name]
[name]
Contact: [name]
[contact] [name]
E-mail: [contact]

REGULATORY AND CLINICAL CONSULTANT

Cawthon Clinical Consulting
[name]
[name]
Contact: [name], BS, MS, EMT-P
Principal Clinical Consultant
[contact]
E-mail: [contact]

MONITOR

Erchonia Corporation
[name]
[name]
Contact: [name]
[contact] [name]
E-mail: [contact]

PRINCIPAL CLINICAL INVESTIGATORS AND TEST SITES

- [name], DC, RN
Wautier Wellness Chiropractic
[name]
[name]
[contact]
E-mail: [contact]
- [name], DC, DACBN,
New York ChiroCare
[name]
[name]
[contact]
E-mail: [contact]
- [name] DC,
Gair Laser Chiropractic
[name]
[name]
[contact]
Email: [contact]

INSTITUTIONAL REVIEW BOARD

WCG IRB

[name]

[name]

[contact]

WIRB Tracking Num.: 20253018

PURPOSE OF STUDY

The purpose of this clinical study is to evaluate whether pre-treatment with the Erchonia® PPL blue laser therapy, followed sequentially with the standard Erchonia red laser therapy, is non-inferior to (equivalent to or superior to) the standard Erchonia red laser therapy when applied alone in providing temporary relief of nociceptive musculoskeletal pain.

INDICATION FOR USE

The indication (claim) being sought through support of the results of this clinical study is:

“The Erchonia® PPL is indicated for use as a pre-treatment adjunct to enhance the standard Erchonia red laser therapy for the temporary relief of nociceptive musculoskeletal pain.”

It is intended that the results of this clinical study be used to support a 510(k) submission to FDA for clearance to market the device for the intended indication.

EXPECTED RESULTS

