The clinical study that supported clearance of K191257 and K212595 was a single arm (active treatment only), historical comparative design to demonstrate non-inferiority of the standard Erchonia red laser therapy when used in simultaneous combination with violet laser therapy compared with application of the standard Erchonia red laser therapy protocol alone in the temporary reduction of neck and shoulder pain of musculoskeletal origin. The historical comparative active data set for that clinical study used for non-inferiority analysis was the results from the Erchonia® red diode therapy only active subject group attained in the 2001 trial whose results successfully supported 510(k) clearance (K012580) of application of red laser light therapy only for the identical indication. This same historical comparative active data set will be used as the historical comparative Erchonia red laser therapy only active treatment data set for the current proposed clinical study.

SUBJECT GROUP

There will be a single subject group treated in this study. All subjects will receive the active study treatment with the blue laser therapy using the Erchonia® PPL first followed sequentially with the standard Erchonia red laser therapy (*Erchonia XLR8, FDA cleared under K211186*)

Comparative subject data for the red diode alone procedure administration will be taken from the Erchonia 2001 study whose results supported FDA market clearance for K012580.

BLINDING

As all subjects in this study will receive active treatment administrations with the Erchonia® PPL and the Erchonia XLR8, neither subjects nor investigators will be blinded. The statistician analyzing the study results will however be blinded with respect to study success analysis. The data from this combined laser therapy study and the retrospective comparative data from the 2001 red diode only study will be deidentified and presented to the study statistician as 'Group A' and 'Group B'. The statistician will not be aware of which group – A or B – contains the current combined laser therapy data and which contains the retrospective comparative red diode only data.

RANDOMIZATION

As this study is a single treatment group study, randomization to treatment group is not applicable. Therefore, this is a non-randomized trial.

SUBJECTS

Subject Sample

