The primary efficacy outcome measure for this clinical study is identical to that of the comparative reference study and is defined as the change in subject self-reported Visual Analog Scale (VAS) pain rating from baseline to study endpoint evaluation, with study endpoint defined as within 3 minutes of completion of the study single sequential treatment administration with the Erchonia® PPL blue laser therapy followed by the standard Erchonia red laser therapy administered using the Erchonia® XLR8.

Individual Subject Success Criteria

individual subject success criteria is defined as a 30% or greater decrease in self-reported neck and shoulder pain rating on the 0-100 VAS at study endpoint relative to baseline.

Overall Study Success Criteria.

Overall study success criteria is defined as at least 65%±5% of subjects in the current study meeting the study individual subject success criteria.

Justification for Study Success Criteria

The clinical relevance and justification of the individual and overall study success criteria is as follows:

- This study is a non-inferiority study, such that the research hypothesis is that the sequential combination therapy with the Erchonia® PPL blue laser and the standard Erchonia red laser therapy is either equivalent to or superior to the standard Erchonia red diode only therapy in effecting a clinically meaningful reduction in neck and shoulder pain of musculoskeletal origin, based upon the data attained from the red diode only clinical trial conducted in 2001 whose results successfully supported 510(k) clearance of application of the PL3000 red diode only for the identical indication being sought through the results of this clinical trial.
- The individual subject success criteria in this clinical study is identical to that of the comparative reference study.
- The overall study success criteria in this clinical study is based on the actual proportion of individual subject successes attained during the comparative reference trial for the active red diode treatment group, of 65%. The $\pm 5\%$ is the selected equivalence margin (δ), the maximally clinically acceptable difference for which the range of values (60% to 70%) for which the efficacies are “close enough” to be considered equivalent.
- Non-inferiority will be established if the proportion of subjects who attain the individual subject success criteria is no more than 5% less than the reference subject group (i.e. no less than 60%).

Hypotheses

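### The indication claims that the blue laser enhances red laser therapy, but the plan tests only non-inferiority to red alone, a hypothesis that an inert blue laser would satisfy

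*Combined protocol and SAP*

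**What the plan says.** Indication for Use states the claim that the results are meant to support: the PPL is "indicated for use as a pre-treatment adjunct to enhance the standard Erchonia red laser therapy". Regulatory Background also gives better therapeutic outcomes as the goal of the pre-treatment.

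Purpose of Study sets a different question: whether blue followed by red "is non-inferior to (equivalent to or superior to) the standard Erchonia red laser therapy when applied alone". Justification for Study Success Criteria repeats it: the research hypothesis is that the combination "is either equivalent to or superior to the standard Erchonia red diode only therapy".

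On treatment, Subject Group says of the two lasers: "All subjects will receive the active study treatment with the blue laser therapy using the Erchonia® PPL first followed sequentially with the standard Erchonia red" (the sentence goes on to name the XLR8). The Treatment Administration Protocol adds: "The red laser therapy treatment administration protocol is identical to that in the retrospective comparative control study". The justification for that protocol says: "The only modification in the current study is the addition of a 5-minute treatment with the Erchonia PPL laser".

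On the comparator: "Comparative subject data for the red diode alone procedure administration will be taken from the Erchonia 2001 study". There is no concurrent red-only or sham-blue arm, and under Blinding, "neither subjects nor investigators will be blinded".

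Hypotheses gives H0: P ≤ 60% and H1: P > 60%, where P is the responder rate in the current study. Under Change Scores there is also a two-sample t-test on mean VAS change at p < 0.05. Its stated purpose is to assess equivalency in support of the responder result. Secondary Evaluations are descriptive only.

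**The concern.** Non-inferiority is the natural question when a new treatment replaces an active one. Here blue is added to the whole red treatment. If blue does nothing, blue plus red performs like red alone, and like red alone meets the objective. An enhancement claim says that blue plus red is better than red alone, and no analysis in the plan has the job of showing that.

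At stake is what a successful trial may be said to have found. Meeting the stated criterion would not separate a PPL that adds benefit from one that adds nothing, so the trial could succeed on its own terms and still leave the indication it was run for unsupported.

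**Working it through.** **Inputs**
- Current sample size: 43 (Sample Size), copied from the reference active arm rather than derived from power.
- Red-alone responder rate: 65.1% (Supporting Erchonia Corporation Clinical Data, item 1), with 43 subjects in that arm (item 2).
- Margin: 5 percentage points, giving a 60% floor (Justification for Study Success Criteria).
- Assumption: the 2001 red-alone rate carries over to the current sites, subjects and red device.

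**Reproducing the plan's figure.** 28/43 = 0.6512, the stated 65.1%. The plan rounds this to 65%, and 65% − 5% = 60%.

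**Is H1 true with an inert PPL?** With no blue effect, P is about 0.651. Since 0.651 > 0.60, H1 holds.

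**How often would an inert PPL pass?** The plan does not name a test for the responder proportion, so three readings are shown. X is the number of responders out of 43 and follows a binomial distribution: P(X ≥ k) = Σ from j = k to 43 of C(43, j) p^j (1 − p)^(43 − j).

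| Reading of the success rule | Needed | p = 0.65 | p = 28/43 |
|---|---|---|---|
| Observed rate no less than 60% | 26/43 (60.5%) | 0.785 | 0.790 |
| Observed rate at least 65% | 28/43 (65.1%) | 0.563 | 0.570 |
| Exact one-sided 5% test of P ≤ 60% | 32/43 (74.4%) | 0.127 | 0.130 |

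For the third row, P(X ≥ 32) at p = 0.60 is 0.035, and 31/43 would give 0.070. These probabilities treat all 43 subjects as evaluable. The added requirement that ITT and PP agree could lower them.

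**What would each threshold say about enhancement?** Compare it with 28/43 in 2001, using Newcombe 95% intervals for the difference.

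| Current result | Difference | 95% interval |
|---|---|---|
| 28/43 | 0 | −0.195 to 0.195 |
| 32/43 | 4/43 = 0.093 | −0.099 to 0.277 |
| 35/43 | 7/43 = 0.163 | −0.025 to 0.336 |
| 36/43 | 8/43 = 0.186 | 0.001 to 0.356 |

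At 26/43 the observed rate is below the 2001 rate. At 28/43 the difference is zero. At 32/43 the strictest reading rejects 60% but not equality with red alone. A lower limit above zero first appears at 36/43 (83.7%) by Newcombe. The Agresti–Caffo lower limit at 36/43 is −0.001, so that method needs 37/43.

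**Chance of reaching 36/43**, holding the 2001 count at 28 and using assumed true rates: P(X ≥ 36) = 0.03 at 70%, 0.12 at 75% and 0.35 at 80%.

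**The case against.** **The aim is stated openly, and superior results count.** Purpose of Study, Expected Results and the SAP all describe the objective as equivalent or superior. That is fair, and the mismatch is narrow: it lies in the enhancement wording of the indication and in the matching goal under Regulatory Background. But equivalent is the no-enhancement case, and it counts as success.

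**The same design supported the red/violet clearances.** Study Justification says so. The indications quoted for those clearances are for temporary relief, and none of them claims enhancement. The precedent therefore does not reach this wording. What the regulator would accept cannot be judged from these documents.

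**The plan does contain a between-group test.** A reader might infer that the two groups are never formally compared for a difference. That would be wrong: the first bullet under Change Scores specifies a t-test of the difference in mean VAS change, and the primary measure is itself defined as VAS change. What stands is that no superiority hypothesis or decision rule is attached to that test, and its stated role is to support an equivalency conclusion.

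**An inert PPL is not certain to pass.** A reader might infer that it is. The documents support only that the hypothesis would be true. The chance of passing ranges from about 13% to 79% with the reading of the rule, and all these figures assume that the 2001 rate carries over.

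**A win over the 2001 arm would settle it.** A reader might infer this too, but it does not follow. The 2001 trial was double-blind and used the older PL3000. The current one is open label, uses the XLR8, and rests on a self-rated VAS within three minutes of treatment. Expectation, population or device differences could raise the rate with no contribution from blue.

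**Conclusion.** The point holds as a mismatch between the claim and the hypothesis. The indication asserts added benefit, while the only decision rule is P > 60% against a red-alone rate of 65.1%. If the 2001 rate carries over, an inert PPL makes H1 true. It passes with probability of about 79%, 56–57% or 13%, according to whether 26, 28 or 32 responders are needed. None of those thresholds demonstrates enhancement.

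The conclusion does not depend on which reading of the rule is adopted, because even the strictest one rejects only 60%. The probabilities do depend on it, and on the carry-over assumption. It would go too far to say that the trial has no value or that a better result is impossible. The supportable statement is that meeting the planned criterion does not support an enhancement claim.

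**What to change.** 1. **Align the claim with the test.** In Indication for Use and in the SAP, state that meeting the success criterion supports only that adding PPL did not reduce the response to red laser by more than the margin. Remove the enhancement wording from the claim that this result supports, and make the goal under Regulatory Background consistent.

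2. **Optionally, pre-specify a superiority comparison.** Once non-inferiority is met, compare the responder rate with the 2001 red-only arm and require a lower 95% limit above zero. Name the interval method in advance (Newcombe needs 36/43, Agresti–Caffo 37/43). Report the low chance of reaching 36/43: about 3%, 12% or 35% at assumed true rates of 70%, 75% or 80%. As a second step in a fixed sequence it needs no extra alpha. Label it as a minimum condition and supportive only. A positive result cannot by itself be attributed to PPL or described as proof of enhancement, since it sets an open-label trial against a double-blind historical arm with an older red device.

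The cost is wording and, if the second step is taken, one analysis of data already planned. The downside is plain: the enhancement claim is not supported by this trial as designed. Attributing a gain to PPL would take a concurrent comparison with sham blue, which is a redesign and is not required for either step above.
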